17.1 Sample Size

This study is intended to be a pilot study that will be used to obtain initial data on the feasibility and safety of VentFree to assist in the process of ventilator weaning. The primary outcome of this study is the effect of abdominal NMES on respiratory muscle strength over time. There is currently no data in the literature to support a sample size calculation for this study. Given this constraint, in this pilot study a total of 24 participants was deemed adequate and is consistent with sample size recommendations in the literature.¹ Allowing for a 10% drop out rate, up to 26 participants will be recruited for this study. The data collected on the secondary endpoints will be used to determine the participants needed for a future randomized controlled trial of the device on weaning outcome.

18 Data Collection, Retention and Monitoring

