Each participant will receive either active or placebo electrical muscle stimulation to the abdominal wall during exhalation for sixty minutes per day, five days per week for the shorter of six weeks or until the patient is weaned from mechanical ventilation. Participants will be assigned to active or placebo stimulation in random order (using a random number generator). Evaluations will be performed at baseline, after three weeks of treatment and at the end of treatment. A flow diagram of the study protocol is shown in Figure 3

[figure not shown]

Figure 3 Study Flow Diagram

The maximum duration of participant participation is 45 days. The total duration of the study is expected to be 6 months.

7 Outcome Measures

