7.1 Primary Outcome Measures

The primary outcome measure in this study is:

- **Maximum Expiratory and Inspiratory Pressure** – The strength of the inspiratory and expiratory muscles will be assessed using the maximum inspiratory pressure and maximum expiratory pressure test respectively.

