11.9 Maximum Expiratory Pressure and Maximum Inspiratory Pressure

Maximum Expiratory Pressure (MEP) and Maximum Inspiratory Pressure (MIP) will be measured at the Baseline Visit, Intermediate Visit, and Final Visit using a cuff inflated cannula as described by Vitacca et al.²¹

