12.6 Early Withdrawal Visit

In the case that the patient withdraws or is withdrawn from the protocol (see Section 14) before the end of the intervention period, and providing the patient consents, then the investigators will perform and record the participant's MEP, MIP, thickness of the abdominal wall muscles and diaphragm, CPF, resting breathing parameters and adverse events related to stimulation or otherwise.

If the participant is withdrawn from the study because they have successfully weaned from mechanical ventilation then the study researcher will also calculate and record the number of days taken to wean taken from the institution of mechanical ventilation.

13 Adverse Experience Reporting and Documentation

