14.1 Withdrawal of Participants from the Study

A participant may be withdrawn from study treatment at any time if the participant, the investigator, or the Sponsor feels that it is not in the participant's best interest to continue. The following is a list of possible reasons for study treatment discontinuation:

- Successful weaning from mechanical ventilation
- Participant withdrawal of consent
- Participant is not compliant with study procedures
- Adverse event that in the opinion of the investigator would be in the best interest of the participant to discontinue study treatment
- Protocol violation requiring discontinuation of study treatment
- Lost to follow-up
- Sponsor request for early termination of study
- Positive pregnancy test (females)

If a participant is withdrawn from treatment due to an adverse event, the participant will be followed and treated by the PI until the abnormal parameter or symptom has resolved or stabilized.

All participants who discontinue study treatment should come in for an early discontinuation visit as soon as possible.

All participants are free to withdraw from participation at any time, for any reason, specified or unspecified, and without prejudice. This will not affect the care they receive, now or in the future.

Reasonable attempts will be made by the investigator to provide a reason for participant withdrawals. The reason for the participant's withdrawal from the study will be specified in the participant's source documents.

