12.3 Replacement of Participants

While it is estimated that 24 is a suitable sample size for this study, the actual study sample size of 26 allows for a 10% drop out rate. Therefore, up to two participants who withdraw from the study will be replaced.

15 Protocol Violations

A protocol violation occurs when the participant, investigator, or Sponsor fails to adhere to significant protocol requirements affecting the inclusion, exclusion, participant safety and primary endpoint criteria.

Failure to comply with Good Clinical Practice (GCP) guidelines will also result in a protocol violation. The Sponsor will determine if a protocol violation will result in withdrawal of a participant.

When a protocol violation occurs, it will be discussed with the investigator and a Protocol Violation Form detailing the violation will be generated. This form will be signed by a Sponsor representative and the Investigator. A copy of the form will be filed in the site's regulatory binder and in the Sponsor's files.

16 Protocol Amendments

Amendments to the clinical investigation plan must be submitted to the Sponsor for review before submitting to the appropriate IRB for approval.

17 Statistical Methods and Considerations

Only participants who fulfil the protocol in terms of eligibility, interventions and outcome assessment will be included in the statistical analysis. Patient variables will be presented using means and standard deviations for continuous normally distributed variables, medians and interquartile ranges for continuous non-normally distributed variables, and proportions and absolute numbers for categorical variables.

Adverse event rates will be coded by body system and MedDra classification term. Adverse events will be tabulated by treatment group and will include the number of patients for whom the event occurred, the rate of occurrence, and the severity and relationship to study treatment.

Study results will first undergo descriptive level statistical analyses. For continuous variables, Two-way, Student's t-tests will then be carried out using unequal variances where the variables are normally distributed. Tests for normality will be carried out using the Shapiro-Wilk method. Variables that are not normal in distribution that also cannot be log transformed to a normal distribution curve will be analysed using the Mann-Whitney U test or other non-parametric methods to be determined based on actual data distributions.

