In the second level of analysis, we will quantify the magnitude to which abdominal NMES exhibits a protective effect. Crude and adjusted linear regression models will be carried out where the outcome variable is continuous and the covariates are normally distributed or categorical. Our prior experience with measures of respiratory function, which will be measured in this study, indicate that select covariates may need to be controlled for or otherwise do not always fit a normal distribution. Therefore, crude and adjusted generalized linear models are anticipated. These regression models will be carried out at the point of successful wean. All multiple regression covariates, linear or generalized, will be assessed for interaction, collinearity and confounding. For all unadjusted and adjusted multinomial models the overall model log likelihood ratio and Hosmer and Lameshow goodness-of-fit will be conducted to ensure models report significance and are not over fitted. Adjusted regression models will undergo sensitivity analysis and bootstrap analyses. Bootstrap analysis is a re-sampling strategy to estimate the population parameter of interest based on the observed, sample data.

The number of tries to successful wean will be quantified using Poisson regression. Crude and adjusted models will be carried out. Kaplan-Meier survival analysis will be carried out to quantify differences in the time to wean in the treatment abdominal NMES modality compared to the control. As the patients will be resident in hospital facilities, we do not anticipate significant methodological concerns with respect to censoring.

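### The primary outcome is respiratory muscle strength over time, but Section 17 names no method that links a person's repeated MIP and MEP readings and gives no rule for the Day 23 or early-exit readings.

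*Combined protocol and SAP*

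**What the plan says.** Section 17.1 and the synopsis define the target: "The primary outcome of this study is the effect of abdominal NMES on respiratory muscle strength over time". Section 7.1 names the two measures, "The strength of the inspiratory and expiratory muscles will be assessed using the maximum inspiratory pressure and maximum expiratory pressure test respectively", but gives no time point and no change score.

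The readings are repeated. Section 6: "Evaluations will be performed at baseline, after three weeks of treatment and at the end of treatment". Section 11.9: MIP and MEP "will be measured at the Baseline Visit, Intermediate Visit, and Final Visit using a cuff inflated cannula". Section 12.6 adds an exit assessment that includes MIP and MEP for anyone who leaves "before the end of the intervention period, and providing the patient consents, then the investigators will perform and record" it. Section 14.1 lists "Successful weaning from mechanical ventilation" among the reasons for stopping study treatment and says that everyone who stops should have the exit visit. Appendix A agrees for MIP and MEP.

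For continuous outcomes, Section 17 says that "t-tests will then be carried out using unequal variances where the variables are normally distributed", with Mann-Whitney or an unspecified non-parametric alternative otherwise. It then says that "Crude and adjusted linear regression models will be carried out where the outcome variable is continuous", with generalized linear models as a further option, and places these regressions at the point where a participant weans. The analysis is limited to participants who meet the protocol on eligibility, treatment and assessment of outcomes. Sensitivity analyses are mentioned without content.

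**The concern.** The stated outcome is a time course compared between arms. To estimate it, a method must connect the readings of one person and contain an arm-by-time effect. Section 17 names no such method.

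Three practical gaps follow. The time point of the main strength comparison is left open. The Day 23 and exit readings, which the trial pays to collect, have no stated use. And it is unclear whether a person with some but not all readings stays in the analysis.

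The last gap matters because leaving is probably not random. Section 3.2 names reduced respiratory muscle strength as one side of the main mechanism of weaning failure, and weaning ends study treatment. On the protocol's own reasoning, stronger participants tend to leave sooner, and more of them in the active arm if the device works. An analysis that ignores their earlier or exit readings could then understate the effect.

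**Working it through.** **The plan's own figure.** Section 17.1 takes 24 participants, allows 10% drop-out and recruits up to 26. Multiplying, 24 × 1.1 = 26.4, which rounds to 26; dividing, 24 / 0.9 = 26.7, which rounds up to 27. The 26 is reproduced to within one participant. The 24 comes from a rule of thumb, so there is no power figure to reproduce.

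**Matching target, data and method.**

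| Item | Where | Content |
|---|---|---|
| Target | 17.1 | Effect on strength over time |
| Readings | 6, 11.9, 12.6, Appendix A | Baseline, Day 23, Day 45, exit |
| First-level test | 17 | Independent-sample test; time point and scale not stated |
| Regressions | 17 | At weaning; undefined for those who never wean |
| Repeated-measures or mixed model | none | Not named |
| Role of Day 23 and exit readings | none | Not stated |
| Missing readings | 17 | No method; restriction on outcome assessment |

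**Bias, on assumed inputs.** The documents give no SD, correlation or missing rate for MIP or MEP. Assumed: 12 per arm; normal readings with SD 1; true arm difference 0.4 SD at Day 23 and 0.8 SD at Day 45; correlation 0.6 of each visit with baseline and 0.7 between visits. The participants strongest at Day 23 have no later reading in the analysis. Three estimates of the Day 45 difference were simulated:

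- complete-case difference in means;
- complete-case regression on arm and baseline;
- joint estimate = b_arm + b_23 × d_23. Here b_arm and b_23 come from regressing Day 45 on arm, baseline and Day 23 in those with Day 45, and d_23 is the baseline-adjusted Day 23 arm effect in everyone.

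| Missing, active / placebo | Unadjusted | Baseline-adjusted | Joint |
|---|---|---|---|
| 1/3 and 1/6 | 0.64 | 0.71 | 0.80 |
| 1/2 and 1/4 | 0.55 | 0.65 | 0.80 |
| One per arm | 0.79–0.80 | 0.79–0.80 | 0.79–0.80 |

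With 1/3 and 1/6 missing and between-visit correlation varied from 0.6 to 0.8, the baseline-adjusted estimate runs from about 0.74 down to 0.68. In the first row its shortfall is 0.80 − 0.71 = 0.09 SD. The simulated standard error is about 0.38 SD, so the ratio is 0.09 / 0.38 = 0.24.

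**How far the joint model's 0.80 depends on the dropout rule** (1/3 and 1/6 missing):

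| Leaving depends on | Baseline-adjusted | Joint |
|---|---|---|
| Strength at Day 23 | 0.71 | 0.80 |
| Strength midway between visits (an added assumed reading) | 0.67 | 0.72 |
| Strength at Day 45 | 0.62 | 0.66 |
| Strength before Day 23, no later reading | 0.71 | 0.71 |

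**Precision.** With equal correlation ρ between readings and a fraction m missing at random, the variance of the joint estimate relative to the baseline-adjusted one is 1 − m·p², where p = ρ/(1 + ρ). For ρ = 0.5 and m = 0.1, p² = 0.111 and the ratio is 0.989. For ρ = 0.8 and m = 0.5, p² = 0.198 and the ratio is 0.901. Square roots are 0.994 and 0.949, so the standard error falls by about 1% to 5%; simulation put the gain at 1% to 6%. Random losses, or equal fractions lost per arm, gave no bias.

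**Information in Day 23.** At correlation 0.7, Day 23 alone explains 0.7² = 0.49 of the Day 45 variance. Baseline alone explains 0.6² = 0.36. Together they explain (0.36 + 0.49 − 2 × 0.6 × 0.7 × 0.6) / (1 − 0.36) = 0.54, so Day 23 adds about 0.18.

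**The case against.** A reader might infer that the plan compares the arms at Day 45 and discards everyone without a Day 45 reading. The documents do not support that. Section 17 never mentions Day 45. The t-tests have no stated time point or scale, so a change score or a test at each visit is not excluded. Leavers, including those who wean, are due an exit MIP and MEP reading if they consent, and the plan does not say whether it stands in for Day 45. Loss through the outcome-assessment restriction is possible but not stated.

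The simulation gives leavers no exit reading, so it describes what happens if those readings go unused, not what the protocol schedules. Its full recovery to 0.80 reflects dropout made to depend on Day 23 alone. Losses of 25% to 37.5% overall also exceed the 10% allowance, although weaning could raise the number without a Day 45 reading.

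Finally, this is a pilot with no power calculation, and one could regard the choice of model as preference. These objections limit the size of the harm. They do not supply a method for an outcome defined over time, or a rule for readings already scheduled.

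**Conclusion.** The point holds as a gap in specification. No method named in Section 17 links a person's readings or estimates an arm-by-time effect. The regressions at weaning exclude those who never wean, and the Day 23 and exit readings have no assigned role.

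The likely numerical harm is modest and conditional. It needs stronger participants to leave after Day 23, in unequal numbers by arm, with their exit readings unused. A baseline term alone then leaves a shortfall of about 0.06 to 0.12 SD on a true 0.80 SD (one third and one sixth missing), less than one standard error at 12 per arm. A repeated-measures model removes it fully only if leaving is explained by observed readings. Under random or balanced losses the gain is only a slightly smaller standard error. All these sizes rest on assumed effects, correlations and missing fractions.

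The change should be made: it is cheap, and it brings the analysis into line with the stated outcome of a trial meant to inform a follow-up trial.

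**What to change.** In Section 17 and the synopsis:

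1. Make the primary analysis of MIP, and separately of MEP, a linear mixed model for repeated measures with baseline value, arm, time and arm-by-time, and Kenward-Roger degrees of freedom. Name in advance a simple within-person covariance that allows irregular days.
2. Include all randomised participants with any post-baseline MIP or MEP reading. Lift the outcome-assessment restriction for this analysis; otherwise people are removed before the model is fitted.
3. Enter every reading, including exit readings, at its actual study day. This also absorbs the Intermediate Visit timing, which Section 12.3 heads as Day 23 but describes as ideally day 21; those two statements need reconciling.
4. Name the primary contrast, for example the arm difference at the end of the six-week period. Report the Day 23 difference as well, each with a 95% confidence interval.
5. State that for weaned participants any value after their exit reading is predicted by the model.
6. Add a supportive baseline-adjusted comparison of the last on-study reading (Day 45 or exit).

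Cost: wording and standard software, with no new data, visits or participants. The downsides are a missing-at-random assumption, which the dropout scenarios above show can fail, and an assumed shape for the time trend when actual study day is used.

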18.1 Data Collection Instruments

The PI and his research associates will prepare and maintain adequate and accurate source documents designed to record all observations and other pertinent data for each participant treated with the study treatment.

Study personnel at each site will enter data from source documents corresponding to a participant's visit into the protocol-specific paper case report form (CRF) when the information corresponding to that visit is available. Participants will not be identified by name on any study documents to be collected by the Sponsor (or designee), but will be identified by a participant number and initials.

If a correction is made on a CRF, the study staff member will line through the incorrect data, write in the correct data and initial and date the change.

The PI and his research associates are responsible for all information collected on participants enrolled in this study. All data collected during the course of this study must be reviewed and verified for completeness and accuracy by the Investigator. A copy of the CRF will remain at the Investigator's site at the completion of the study.

18.2 Availability and Retention of Investigational Records

The Investigator must make study data accessible to the monitor, other authorized representatives of the Sponsor (or designee), IRB/IEC, and Regulatory Agency (e.g., FDA) inspectors upon request. A file for each participant must be maintained that includes the signed Informed Consent, HIPAA Authorization and copies of all source documentation related to that participant. The Investigator must ensure the reliability and availability of source documents from which the information on the CRF was derived.

All study documents (patient files, signed informed consent forms, copies of CRFs, Study File Notebook, etc.) must be kept secured for a period of two years following the completion of the study. There may be other circumstances for which the Sponsor is required to maintain study records and, therefore, the Sponsor should be contacted prior to removing study records for any reason.

18.3 Monitoring

Monitoring visits will be conducted by representatives of the Sponsor according to the U.S. CFR Title 21 Parts 50, 56, and 312 and ICH Guidelines for GCP (E6). By signing this protocol, the Investigator grants permission to the Sponsor (or designee), and appropriate regulatory authorities to conduct on-site monitoring and/or auditing of all appropriate study documentation.

22 APPENDIX A: SCHEDULE OF EVENTS

	Baseline Day 1	Stimulation Visits Days 2 - 22	Intermediate Visit Day 23	Stimulation Visits Days 24 - 44	Final Visit Day 45	Early Withdrawal
Informed Consent	X					
Randomization	X					
Medical History	X					
Concomitant Medications	X		X		X	X
Complete Physical Exam	X					
Height	X					
Weight	X					
Vital Signs	X					
Oximetry	X					
Expiratory Flow Limitation	X					
APACHE II	X					
Maximum Expiratory Pressure	X		X		X	X
Maximum Inspiratory Pressure	X		X		X	X
Abdominal Wall Thickness	X		X		X	
Diaphragm Thickness	X		X		X	
Cough Peak Flow	X		X		X	X
Tidal Volume	X		X		X	X
Respiratory Rate	X		X		X	X
Minute Ventilation	X		X		X	X
Administration of Stimulation		X		X		
Sensation of Stimulation		X		X		
Adverse Events	X	X	X	X	X	X
Time spent breathing without mechanical ventilation support	X	X	X	X	X	X
Number of Days Taken to Wean						X
